Appendix 4.3 Procedures for Recording Adverse Events

Appendix 4.3.1 Injection Reactions

AEs that occur during or within 24 hours after studied medicinal product administration should be captured as individual signs and symptoms in the AE section of the electronic case report form (eCRF) rather than an overall diagnosis (e.g., record dyspnea and hypotension as separate events rather than a diagnosis of anaphylactic reaction).

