8.1.1.1 Adverse Events

According to the International Council for Harmonisation (ICH), an AE is any untoward medical occurrence in a patient or clinical investigation patient administered a

pharmaceutical product, regardless of causal attribution. An AE can therefore be any of the following:

- Any unfavorable and unintended sign (including an abnormal laboratory finding), symptom, or disease temporally associated with the use of a medicinal product, whether or not considered related to the medicinal product.
- Any new disease or exacerbation of an existing disease (a worsening in the character, frequency, or severity of a known condition), except as described in [Appendix 4](#).
- Recurrence of an intermittent medical condition (e.g., headache) not present at baseline.
- Any deterioration in a laboratory value or other clinical test (e.g., electrocardiogram, x-ray) that is associated with symptoms or leads to a change in study treatment or concomitant treatment or discontinuation from study medicine.

Note: AEs should be reported listing the underlying cause (if known) of the event as the primary event term (see [Appendix 4.3.3](#)).

8.1.1.2 Assessment of Serious Adverse Events (Immediately Reportable to the Marketing Authorization Holder), Non-serious Adverse Events of Special Interest (AESI) and Other Non-serious Adverse Events

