Appendix 4.3.2 Diagnosis versus Signs and Symptoms

For AEs, other than injection reactions (see [Appendix 4.3.1](#)), a diagnosis (if known) should be recorded in the AE section of the eCRF rather than individual signs and symptoms (e.g., record only liver failure or hepatitis rather than jaundice, asterixis, and elevated transaminases). However, if a constellation of signs and/or symptoms cannot be medically characterized as a single diagnosis or syndrome at the time of reporting, each individual event should be recorded in the AE section of the eCRF. If a diagnosis is subsequently established, all previously reported AEs based on signs and symptoms should be nullified and replaced by one AE report based on the single diagnosis, with a starting date that corresponds to the starting date of the first symptom of the eventual diagnosis.

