Appendix 4.3.8 Deaths

All deaths that occur during the protocol-specified AE reporting period (see [Section 8.1.2.1](#)), regardless of relationship to study medicine, must be recorded in the AE section of the eCRF and immediately reported to the MAH (see [Section 8.1.3.1](#)).

Death should be considered an outcome and not a distinct event. The event or condition that caused or contributed to the fatal outcome should be recorded as the single medical concept on the AE section of the eCRF. Generally, only one such event should be reported. The term "**sudden death**" should only be used for the occurrence of an abrupt and unexpected death due to presumed cardiac causes in a patient with or without pre-existing heart disease, within 1 hour after the onset of acute symptoms or, in the case of an unwitnessed death, within 24 hours after the patient was last seen alive and stable. If the cause of death is unknown and cannot be ascertained at the time of reporting, "**unexplained death**" should be recorded on the AE section of the eCRF. If the cause of death later becomes available (e.g., after autopsy), "unexplained death" should be replaced by the established cause of death.

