Appendix 4.3.10 Lack of Therapeutic Efficacy

Events that are clearly consistent with the expected pattern of progression of the underlying disease should not be recorded as AEs. These will be captured as effectiveness assessment data only. In most cases, the expected pattern of progression will be based on review of optical coherence tomography (OCT) results (spectral-domain optical coherence tomography angiography (SD-OCT) or swept-source optical coherence tomography (SS-OCT)). In rare cases, the determination of clinical progression will be based on symptomatic deterioration. However, every effort should be made to document progression through use of objective criteria. If there is any uncertainty as to whether an event is due to disease progression, it should be reported as an AE. This exception from reporting includes events of disease progression with a fatal outcome which are clearly attributable to disease progression.

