Appendix 4.3.11 Hospitalization or Prolonged Hospitalization

Any AE that results in hospitalization or prolonged hospitalization should be documented and reported as an SAE (per the definition of SAE in [Section 8.1.1.2.1](#)), except as outlined below.

The following hospitalization scenarios are not considered to be SAEs:

- Hospitalization for respite care
- Hospitalization for a pre-existing condition provided that all of the following criteria are met:
 - The hospitalization was planned prior to the study or was scheduled during the study when elective surgery became necessary because of the expected normal progression of the disease
 - The patient has not suffered an AE
 - Additional conditions
- Hospitalization solely due to progression of the underlying cancer.

The following hospitalization scenarios are not considered to be SAEs but should be reported as AEs instead:

Hospitalization that was necessary because of the patient’s requirement for outpatient care outside of the normal outpatient clinic operating hours.

Appendix 4.3.12 Overdoses, Misuses, Abuses, Off-Label Use, Occupational Exposure, or Medication Error

Any overdose, misuse, abuse, off-label use, occupational exposure, medication error (including intercepted or potential), or any other incorrect administration of medicine under observation should be noted in the Drug Administration section of the eCRF. Any overdose, abuse, misuse, inadvertent/erroneous administration, medication error (including intercepted or potential), or occupational exposure reports must be forwarded to the MAH with or without an AE.

Reports with or without an AE should be forwarded to the MAH as per non-serious timelines. If the associated AE fulfills the seriousness criteria, the event should be reported to the MAH immediately (i.e., no more than 24 hours after learning of the event, see [Section 8.1.3.1](#)).

For the purpose of reporting cases of suspected adverse reactions, an occupational exposure to a medicine means an exposure to a medicine as a result of one's professional or non-professional occupation.

[figure not shown]

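### Appendix 4.3.1 as worded records every adverse event within 24 hours of an injection as symptoms, so Preferred Term counts for early diagnoses can be understated; 4.3.10 and 4.3.11 also conflict with the rules on deaths and SAEs

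*Protocol*

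**What the plan says.** Three parts of Protocol Appendix 4 are involved.

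- **Split rule (4.3.1).** Adverse events from the injection up to 24 hours afterwards "should be captured as individual signs and symptoms in the AE section of the electronic case report form (eCRF) rather than an overall diagnosis". The heading is about injection reactions and the only example is systemic: dyspnea and hypotension are entered in place of an anaphylactic reaction. The sentence has no restriction to systemic events and no exception for ocular ones.
- **Diagnosis rule (4.3.2).** "a diagnosis (if known) should be recorded in the AE section of the eCRF rather than individual signs and symptoms". Symptom reports are to be nullified and replaced once a diagnosis is established. The rule opens with "For AEs, other than injection reactions" and points back to 4.3.1.
- **Progression exception (4.3.10).** Events clearly consistent with expected progression of the underlying disease are not recorded as adverse events. "This exception from reporting includes events of disease progression with a fatal outcome which are clearly attributable to disease progression".
- **Deaths (4.3.8).** "All deaths that occur during the protocol-specified AE reporting period" must be recorded in the eCRF regardless of relationship to the medicine. Section 8.1.2.2 repeats this and classes every event with a fatal outcome as an SAE.
- **Hospitalization (4.3.11).** The scenarios that are not SAEs include "Hospitalization solely due to progression of the underlying cancer".

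In the main text, Section 8.1.1.2.1 makes an adverse event serious if it requires or prolongs inpatient hospitalization, with no cancer exception. Section 8.1.1.4 declares exemption of specific adverse events from collection not applicable. Section 6.7.3 summarizes incidence and numbers of events by System Organ Class and Preferred Term.

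**The concern.** Safety is a stated objective, and its tables are built from the term that the site enters. Faricimab is given into the eye, so the 24-hour window reopens after each injection. Section 8.1.1.2.2 names endophthalmitis as an example under the ocular events of special interest. If a site follows 4.3.1 literally, such a diagnosis with onset in the window is entered as several symptoms and does not appear in its own row. An analysis plan cannot reliably rebuild a diagnosis that was never entered as a term.

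The other two items raise a different problem. A site cannot obey both 4.3.10 and 4.3.8 for a death attributed to disease progression. The cancer item gives an instruction with no referent in a study of nAMD and DME. Both leave the recording of some deaths and the seriousness of some hospitalizations open to interpretation.

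**Working it through.** The protocol states no figure on this point to reproduce. The check is a comparison of the passages, followed by one illustration.

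**1. Scope of the split rule.** The heading of 4.3.1 suggests a narrow class of reactions. The operative sentence defines the class by time alone: during or within 24 hours after administration. An ocular diagnosis with onset at, say, 20 hours falls inside it.

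**2. Whether a later diagnosis repairs the entry.** The replacement step is part of 4.3.2, whose scope excludes injection reactions and refers to 4.3.1 for them. On a plain reading, an event split under 4.3.1 stays split after the diagnosis is known.

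**3. Effect on the tables.** Let D be the true number of cases of a diagnosis, q the share with onset within 24 hours of an injection, and k the number of symptoms entered per split case. If sites follow 4.3.1 as written:

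- Count under the diagnosis term = D × (1 − q), a relative understatement of q.
- Symptom events added = k × q × D.
- Net change in the total number of events = (k − 1) × q × D.

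The protocol gives neither q nor k. The range for q is:

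| q (assumed) | Understatement of the diagnosis term |
|---|---|
| 0 | 0% |
| 0.5 | 50% |
| 1 | 100% |

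For one early case entered as three symptoms (D = 1, q = 1, k = 3, all assumed), the diagnosis count is 1 × (1 − 1) = 0, the symptom events are 3 × 1 × 1 = 3, and the total rises by (3 − 1) × 1 × 1 = 2. The number of eyes or patients with any adverse event does not change.

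**4. Deaths.** 4.3.10 takes fatal progression events out of adverse event recording. 4.3.8 and 8.1.2.2 put all deaths in the reporting period into it. The conflict therefore lies within Appendix 4 as well as between it and Section 8. Section 8.1.2.2 mentions fatal reactions that may not need expedited reporting and points to Section 8.3 for them. Section 8.3 covers product complaints without adverse events, so the pointer resolves nothing.

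**5. Cancer item.** The indications are nAMD and DME, so no underlying cancer is under study. The item could act only on a comorbid cancer. There it would remove SAE status from a hospitalization that 8.1.1.2.1 makes serious.

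**6. Progression and Section 8.1.1.4.** Section 8.1.1.1 itself defers to Appendix 4 for exacerbation of existing disease, so the main text anticipates the non-fatal exception in 4.3.10. It still sits badly with 8.1.1.4, under which no exemptions from collection apply.

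**The case against.** The strongest reply is that the split rule is a deliberate, cross-referenced exception. Section 8.1.2.2 lists injection-related reactions and diagnosis versus symptoms as separate instructions, 4.3.2 carves the former out by name, and the example is systemic. Several safeguards also exist. Severity and seriousness are judged for each recorded event (8.1.1.2.1). Ocular events of special interest are defined by criteria and not by the recorded term (8.1.1.2.2), and the eCRF has a field for them (Table 1). Follow-up reports of SAEs and events of special interest must include a change in diagnosis and narrative information (8.1.3.1), and the marketing authorization holder may make its own medical assessment (8.1.4.2).

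Most of this stands, and it limits the consequence. An early endophthalmitis can still be flagged and reported. But a flag on a symptom does not restore the diagnosis row in a Preferred Term table, and an intended exception for systemic reactions should not be worded to cover all events.

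A reader might infer four stronger points that the protocol does not support.

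- **That Section 8.1.1.1 orders the opposite of 4.3.1.** Its note, "AEs should be reported listing the underlying cause (if known) of the event as the primary event term", refers to Appendix 4.3.3, which deals with events secondary to other events and not with diagnosis versus symptoms.
- **That events or deaths disappear.** Splitting relabels events. For deaths, 4.3.10 reaches only those clearly attributable to progression of the underlying disease, a narrow class in nAMD and DME. It also requires any uncertain event to be reported.
- **That 8.1.1.4 contradicts the cancer item.** It concerns collection, while 4.3.11 concerns seriousness. Worsening of a pre-existing condition remains an adverse event under 4.3.9.
- **That the loss can be put at a definite percentage.** Any such figure needs an incidence and an early-onset share that the protocol does not give.

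**Conclusion.** The point holds as a defect in the site recording rules. The wording of 4.3.1, together with the carve-out in 4.3.2, can understate a diagnosis under its own Preferred Term when onset is within 24 hours of an injection, and can raise symptom event counts. The size for a given diagnosis equals the unknown early-onset share, from 0% to 100%. This assumes that sites follow the text literally.

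The fatal-outcome sentence in 4.3.10 contradicts 4.3.8 and 8.1.2.2, and the cancer item in 4.3.11 is misplaced. Both have narrow reach, and the protocol does not show that either would lower the reported numbers of deaths or SAEs to a material extent. Correction is warranted because it is cheap and the first defect cannot be repaired reliably at the analysis stage.

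**What to change.** - **4.3.1 and 4.3.2:** reword 4.3.1 so that a known or later established diagnosis is the recorded term with its onset date, and symptoms go in the narrative. Align the carve-out in 4.3.2 so that the replacement step also applies to events within 24 hours of an injection.
- **4.3.10:** reconcile the fatal-outcome sentence with 4.3.8 and 8.1.2.2, and correct the pointer to Section 8.3. Align the remaining progression exception with 8.1.1.4, since removing the fatal-outcome sentence alone would leave that inconsistency.
- **4.3.11:** delete the cancer item.

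The cost is a few sentences in the protocol, an update to the eCRF completion guide, and possibly a few more SAE reports.

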Appendix 4.3.2 Diagnosis versus Signs and Symptoms

For AEs, other than injection reactions (see [Appendix 4.3.1](#)), a diagnosis (if known) should be recorded in the AE section of the eCRF rather than individual signs and symptoms (e.g., record only liver failure or hepatitis rather than jaundice, asterixis, and elevated transaminases). However, if a constellation of signs and/or symptoms cannot be medically characterized as a single diagnosis or syndrome at the time of reporting, each individual event should be recorded in the AE section of the eCRF. If a diagnosis is subsequently established, all previously reported AEs based on signs and symptoms should be nullified and replaced by one AE report based on the single diagnosis, with a starting date that corresponds to the starting date of the first symptom of the eventual diagnosis.

Appendix 4.3.3 Adverse Events Occurring Secondary to Other Events

In general, AEs that are secondary to other events (e.g., cascade events or clinical sequelae) should be identified by their primary cause, with the exception of severe or serious secondary events. A medically significant secondary AE that is separated in time from the initiating event should be recorded as an independent event in the AE section of the eCRF. For example:

- If vomiting results in mild dehydration with no additional treatment in a healthy adult, only vomiting should be reported on the eCRF.
- If vomiting results in severe dehydration, both events should be reported separately on the eCRF.
- If a severe gastrointestinal hemorrhage leads to renal failure, both events should be reported separately on the eCRF.
- If dizziness leads to a fall and subsequent fracture, all 3 events should be reported separately on the eCRF.
- If neutropenia is accompanied by an infection, both events should be reported separately on the eCRF.

All AEs should be recorded separately in the AE section of the eCRF if it is unclear as to whether the events are associated.

Appendix 4.3.4 Persistent or Recurrent Adverse Events

A persistent AE is one that extends continuously, without resolution, between patient evaluation time points. Such events should only be recorded once in the AE section of the eCRF. The initial severity (intensity or grade) of the event will be recorded at the time the event is first reported. If a persistent AE becomes more severe, the most extreme severity should also be recorded in the AE section of the eCRF. If the event becomes

serious, it should be reported to the MAH immediately (i.e., no more than 24 hours after learning that the event became serious; see [Section 8.1.3.1](#) for reporting instructions). The AE section of the eCRF should be updated by changing the event from "non-serious" to "serious," providing the date that the event became serious, and completing all data fields related to SAEs.

A recurrent AE is one that resolves between patient evaluation timepoints and recurs subsequently. Each recurrence of an AE should be recorded separately in the AE section of the eCRF.

Appendix 4.3.5 Abnormal Laboratory Values

Not every laboratory abnormality qualifies as an AE. A laboratory test result must be reported as an AE if it meets any of the following criteria:

- Is accompanied by clinical symptoms
- Results in a change in study treatment (e.g., dosage modification, treatment interruption, or treatment discontinuation)
- Results in a medical intervention (e.g., potassium supplementation for hypokalemia) or a change in concomitant therapy
- Is clinically significant in the physician's judgment

It is the physician's responsibility to review all laboratory findings. Medical and scientific judgment should be exercised in deciding whether an isolated laboratory abnormality should be classified as an AE.

If a clinically significant laboratory abnormality is a sign of a disease or syndrome (e.g., alkaline phosphatase and bilirubin $5 \times$ the upper limit of normal [ULN] associated with cholestasis), only the diagnosis (i.e., cholestasis) should be recorded in the AE section of the eCRF.

If a clinically significant laboratory abnormality is not a sign of a disease or syndrome, the abnormality itself should be recorded in the AE section of the eCRF, along with a descriptor indicating if the test result is above or below the normal range (e.g., "elevated potassium," as opposed to "abnormal potassium"). If the laboratory abnormality can be characterized by a precise clinical term per standard definitions, the clinical term should be recorded as the AE. For example, an elevated serum potassium level of 7.0 mEq/L should be recorded as "hyperkalemia."

Observations of the same clinically significant laboratory abnormality from visit to visit should only be recorded once in the AE section of the eCRF (see [Appendix 4.3.4](#) for details on recording persistent AEs).

Appendix 4.3.6 Abnormal Vital Sign Values

Not every vital sign abnormality qualifies as an AE. A vital sign result must be reported as an AE if it meets any of the following criteria:

- Is accompanied by clinical symptoms
- Results in a change in study treatment (e.g., dosage modification, treatment interruption, or treatment discontinuation)

Faricimab—F. Hoffmann-La Roche Ltd

Protocol MR45586, Version 1.0

- Results in a medical intervention or a change in concomitant therapy
- Is clinically significant in the physician's judgment

It is the treating physician's responsibility to review all vital sign findings. Medical and scientific judgment should be exercised in deciding whether an isolated vital sign abnormality should be classified as an AE.

If a clinically significant vital sign abnormality is a sign of a disease or syndrome (e.g., high blood pressure), only the diagnosis (i.e., hypertension) should be recorded in the AE section of the eCRF.

Observations of the same clinically significant vital sign abnormality from visit to visit should only be recorded once in the AE section of the eCRF (see [Appendix 4.3.4](#) for details on recording persistent AEs).

Appendix 4.3.7 Abnormal Liver Function Tests

The finding of an elevated ALT or AST ($> 3 \times$ the ULN) in combination with either an elevated total bilirubin ($> 2 \times$ the ULN) or clinical jaundice in the absence of cholestasis or other causes of hyperbilirubinemia is considered to be an indicator of severe liver injury. Therefore, physicians must report the occurrence of either of the following as an AE:

- Treatment-emergent ALT or AST $> 3 \times$ ULN in combination with total bilirubin $> 2 \times$ the ULN
- Treatment-emergent ALT or AST $> 3 \times$ ULN in combination with clinical jaundice

The most appropriate diagnosis or (if a diagnosis cannot be established) the abnormal laboratory values should be recorded in the AE section of the eCRF (see [Appendix 4.3.5](#)) and reported to the MAH immediately (i.e., no more than 24 hours after learning of the event) either as an SAE or a non-serious AE of special interest (see [Section 8.1.3.1](#)).

Appendix 4.3.8 Deaths

All deaths that occur during the protocol-specified AE reporting period (see [Section 8.1.2.1](#)), regardless of relationship to study medicine, must be recorded in the AE section of the eCRF and immediately reported to the MAH (see [Section 8.1.3.1](#)).

Death should be considered an outcome and not a distinct event. The event or condition that caused or contributed to the fatal outcome should be recorded as the single medical concept on the AE section of the eCRF. Generally, only one such event should be reported. The term "**sudden death**" should only be used for the occurrence of an abrupt and unexpected death due to presumed cardiac causes in a patient with or without pre-existing heart disease, within 1 hour after the onset of acute symptoms or, in the case of an unwitnessed death, within 24 hours after the patient was last seen alive and stable. If the cause of death is unknown and cannot be ascertained at the time of reporting, "**unexplained death**" should be recorded on the AE section of the eCRF. If the cause of death later becomes available (e.g., after autopsy), "unexplained death" should be replaced by the established cause of death.

